		Yea 1 2	Year 1 2 3	Year 1 1 2 3 4	Year 1 1 1 2 3 4 1 	Year 1 Yea 1 2 3 4 1 2 	Year 1 Year 2 1 2 3 4 1 2 3 1 2 3 4 1 2 3 1 2 3 4 1 2 3 1 2 3 4 1 2 3 1 2 3 4 1 2 3 1 2 3 4 1 2 3 1 3 4 1 2 3 4 1 2 3 1 3 3 4 3 4 3 4 3 4 3 4 <td< td="">Year 1 Year 2 1 2 3 4 1 2 3 4 1 2 3 4 1 2 3 4 1 2 3 4 1 2 3 4 1 2 3 4 1 2 3 4 1 2 3 4 1 2 3 4 1 3 4 3 4 3 4 3 4 1 3 4 3 4 3 4 3 4 1 4 <td< td="">Year 1 Year 2 N 1 2 3 4 1 2 3 4 1 1 2 3 4 1 2 3 4 1 1 2 3 4 1 2 3 4 1 1 2 3 4 1 2 3 4 1 1 2 3 4 1 2 3 4 1 1 2 3 4 1 2 3 4 1 1 3 4 3 <td< td="">Year 1 Year 2 Yea 1 2 3 4 1 2 3 4 1 2 1 2 3 4 1 2 3 4 1 2 1 2 3 4 1 2 3 4 1 2 1 2 3 4 1 2 3 4 1 2 1 2 3 4 1 2 3 4 1 2 1 2 3 4 1 2 3 4 1 2 1 3 4 3 4 3 4 3 4 3 4 3 4 3 4 3 4 3 4 3 4 3 4 3 4 3 4 3 4 3 4 3 4 3 4 3 <	Year 1 Year 2 Year 3 1 2 3 4 1 2 3 4 1 2 3 1 2 3 4 1 2 3 4 1 2 3 1 2 3 4 1 2 3 4 1 2 3 1 2 3 4 1 2 3 4 1 2 3 1 2 3 4 1 2 3 4 1 2 3 1 3 4 1 2 3 4 1 2 3 1 3 4 3 4 3 4 3 4 3 4 3 4 3 4 3 4 3 4 3 4 3 4 3 4 3 4 3 4 3 4	</td<>	</td<>	</td<>	Year 1 Year 2 1 2 3 4 1 2 3 4 1 2 3 4 1 2 3 4 1 2 3 4 1 2 3 4 1 2 3 4 1 2 3 4 1 2 3 4 1 2 3 4 1 3 4 3 4 3 4 3 4 1 3 4 3 4 3 4 3 4 1 4 <td< td="">Year 1 Year 2 N 1 2 3 4 1 2 3 4 1 1 2 3 4 1 2 3 4 1 1 2 3 4 1 2 3 4 1 1 2 3 4 1 2 3 4 1 1 2 3 4 1 2 3 4 1 1 2 3 4 1 2 3 4 1 1 3 4 3 <td< td="">Year 1 Year 2 Yea 1 2 3 4 1 2 3 4 1 2 1 2 3 4 1 2 3 4 1 2 1 2 3 4 1 2 3 4 1 2 1 2 3 4 1 2 3 4 1 2 1 2 3 4 1 2 3 4 1 2 1 2 3 4 1 2 3 4 1 2 1 3 4 3 4 3 4 3 4 3 4 3 4 3 4 3 4 3 4 3 4 3 4 3 4 3 4 3 4 3 4 3 4 3 4 3 <	Year 1 Year 2 Year 3 1 2 3 4 1 2 3 4 1 2 3 1 2 3 4 1 2 3 4 1 2 3 1 2 3 4 1 2 3 4 1 2 3 1 2 3 4 1 2 3 4 1 2 3 1 2 3 4 1 2 3 4 1 2 3 1 3 4 1 2 3 4 1 2 3 1 3 4 3 4 3 4 3 4 3 4 3 4 3 4 3 4 3 4 3 4 3 4 3 4 3 4 3 4 3 4	</td<>	</td<>	Year 1 Year 2 N 1 2 3 4 1 2 3 4 1 1 2 3 4 1 2 3 4 1 1 2 3 4 1 2 3 4 1 1 2 3 4 1 2 3 4 1 1 2 3 4 1 2 3 4 1 1 2 3 4 1 2 3 4 1 1 3 4 3 <td< td="">Year 1 Year 2 Yea 1 2 3 4 1 2 3 4 1 2 1 2 3 4 1 2 3 4 1 2 1 2 3 4 1 2 3 4 1 2 1 2 3 4 1 2 3 4 1 2 1 2 3 4 1 2 3 4 1 2 1 2 3 4 1 2 3 4 1 2 1 3 4 3 4 3 4 3 4 3 4 3 4 3 4 3 4 3 4 3 4 3 4 3 4 3 4 3 4 3 4 3 4 3 4 3 <	Year 1 Year 2 Year 3 1 2 3 4 1 2 3 4 1 2 3 1 2 3 4 1 2 3 4 1 2 3 1 2 3 4 1 2 3 4 1 2 3 1 2 3 4 1 2 3 4 1 2 3 1 2 3 4 1 2 3 4 1 2 3 1 3 4 1 2 3 4 1 2 3 1 3 4 3 4 3 4 3 4 3 4 3 4 3 4 3 4 3 4 3 4 3 4 3 4 3 4 3 4 3 4	</td<>	Year 1 Year 2 Yea 1 2 3 4 1 2 3 4 1 2 1 2 3 4 1 2 3 4 1 2 1 2 3 4 1 2 3 4 1 2 1 2 3 4 1 2 3 4 1 2 1 2 3 4 1 2 3 4 1 2 1 2 3 4 1 2 3 4 1 2 1 3 4 3 4 3 4 3 4 3 4 3 4 3 4 3 4 3 4 3 4 3 4 3 4 3 4 3 4 3 4 3 4 3 4 3 <	Year 1 Year 2 Year 3 1 2 3 4 1 2 3 4 1 2 3 1 2 3 4 1 2 3 4 1 2 3 1 2 3 4 1 2 3 4 1 2 3 1 2 3 4 1 2 3 4 1 2 3 1 2 3 4 1 2 3 4 1 2 3 1 3 4 1 2 3 4 1 2 3 1 3 4 3 4 3 4 3 4 3 4 3 4 3 4 3 4 3 4 3 4 3 4 3 4 3 4 3 4 3 4

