The High Intensity exercise to Promote Accelerated improvements in Cardior Espiratory fitness (HI-PACE) study will evaluate the effect of exercise intensity on CRF and insulin sensitivity in obese (BMI: 30-45) African Americans (40-65 yrs.) with at least 1 additional T2D risk factor. Participants (n=60) will be recruited in collaboration with the ECU Center for Health Disparities, and subsequently randomized to moderate intensity (MOD-INT, n=20) or high intensity (HIGH-INT, n=20) aerobic exercise training, or to a control group (CON, n=20) for 24 weeks. Supervised exercise training will be performed at a heart rate associated with ~50% and ~75% of VO₂ max in the MOD-INT and the HIGH-INT groups, respectively at the same exercise volume of 600 MET-minutes per week (consistent with public health recommendations). The primary outcome is the change in CRF, which will be assessed at baseline, mid-intervention, and follow-up. Insulin sensitivity will be measured via an intravenous glucose tolerance test at baseline and follow-up. Other secondary measures include mitochondrial oxidative capacity using infrared and measurements on muscle biopsies (PGC-1 α and other indices of mitochondrial content), the expression of a protein involved with insulin action (GLUT-4 expression) in skeletal muscle as well as systemic inflammation, adiposity, quality of life and exercise enjoyment measures.

Specific Aims: We seek to provide evidence in obese African American that:

- High intensity aerobic training will lead to greater increase in CRF compared with moderate intensity
 aerobic exercise
- High intensity aerobic exercise training will lead to greater improvements in insulin sensitivity compared with moderate intensity aerobic exercise

In accordance with the intent of this mechanism, the HI-PACE study will provide clinically relevant (CRF/insulin sensitivity) and mechanistic data (skeletal muscle), allow us to power outcome variables, and provide recruitment, retention and exercise adherence rates in African Americans for a future R01 proposal.

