Inclusion/exclusion criteria: We will recruit obese (30-45 kg/m²) African Americans (age: 40-65 yrs.) with one additional T2D risk factor. Selection of these risk factors are based on a position stand from the ADA⁵⁰, which provided definitions for impaired fasting glucose, and additional risk factors which are associated with increased risk for T2D (Triglycerides (TG) \geq 150mg/dL, HDL-C < 50 mg/dL or taking cholesterol lowering medications, Blood pressure: systolic \geq 130 mmHG or diastolic \geq 85 mmHg or the use of BP medication, Fasting glucose 100-125 mg/dL, waist circumference \geq 88cm). All participants must be sedentary/low active (step count \leq 6,500 step/day) and not participating in exercise training (\geq 20 minutes on \geq 3 days per week for the last 3 months). We will exclude participants with diagnosed T2D (or blood glucose value>125 mg/dL) or known cardiovascular diseases, excessively high resting blood pressure (systolic >180 mmHg and diastolic >100 mmHg), significant medical conditions, life threatening conditions, pregnancy or plans to become pregnant, conditions that are contraindicated for exercise. In addition, we will exclude individuals who have plans to diet or engage in weight loss, or demonstrate non-compliance during screening visits. Primary Outcome- CRF: We have selected CRF as the primary outcome measurement due to the wellestablished association between CRF levels and T2D⁴⁻⁷. We will measure CRF by maximal oxygen consumption from a maximal exertion treadmill test, which is considered the gold standard technique. Maximal Exercise Test: We will use a modified Balke treadmill (Trackmaster 425, Carefusion, Newton Kansas) protocol to determine CRF, and the appropriate heart rate range for aerobic exercise training. Participants will walk at an initial speed of 2.0 mph with 0% grade for the first 2 minutes after which the treadmill speed will increase to 3.0 mph for the next 2 minutes. Treadmill grade will be increased by 2.5% every 2 minutes until volitional exhaustion. Respiratory gases (VO₂, CO₂) and ventilation will be measured continuously using a True Max 2400 Metabolic Measurement Cart (Parvomedics, Salt Lake City, Utah). **Secondary outcomes**: The majority of secondary measures will be evaluated at baseline and follow-up. Exceptions to this are anthropometry, CRF, and weight data which will also be evaluated at mid-intervention (see Figure 3), and exercise enjoyment/affective valence measures which will occur during exercise sessions. **IVGTT:** Insulin sensitivity will be assessed at baseline and follow-up (24 hours following the last exercise session in exercise groups). After the collection of fasting blood samples, glucose (50%) will be injected into a catheter placed in the antecubital vein at a dose of 0.3 g/kg body weight. Subsequently, blood samples will be obtained at the following time points: 2, 3, 4, 5, 6, 8, 10, 12, 14, 16, 19, 22, 25, 30, 40, 50, 60, 70, 80, 90, 100, 120, 140, 160, and 180 min. Insulin will be injected at minute 20 of the test at a dose of 0.025 U/kg body mass. Blood samples will be centrifuged, and stored at -80°C until sample analysis for glucose and insulin. insulin sensitivity index will be determined through a minimal model ⁵¹.

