Other secondary measures: Body weight will be evaluated a calibrated scale, with the participant fasted and wearing only a hospital gown. Dual Energy X-ray Absorptiometry (DEXA) will be used to measure body composition (fat and lean mass). C-reactive protein (CRP) will be measured using standard analytical techniques. Waist circumference will be evaluated with a gulick tape measure, and recorded at the natural waist. Quality of life (QOL) will be measured by the short form health survey (SF-36)⁵⁷. Exercise enjoyment will be assessed via a 5-item short version of the commonly used Physical Activity Enjoyment Scale (PACE)^{58,59} and will be during exercise training sessions. Affective valance (pleasure/displeasure) will be assessed during exercise training from -5 (very bad) to +5 (very good) with 0 representing neutral feelings. **4. Recruitment:** Participants will be recruited primarily through the ECU Center of Health Disparities (CHD) (directed by [name]., letter of support included). The Community Core of the CHD specializes in recruiting African Americans for research and clinical trials. The Core produces expertly-designed, culturally-tailored recruitment flyers, DVDs, CDs etc., and distributes these through community partners. Using these strategies, the Core has recruited more than **400 African American adults** per year for research. For the present proposal, the Core will design recruitment flyers tailored for African Americans; distribute these in six

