local community settings frequented by them; distribute these to their partners; advertise the project on the Center's African-American community website, Minority Health Matters; and maintain a phone number to answer potential-participants' questions. We will also utilize standard techniques (advertisement, ECU email server, flyering). 5. Pre-screening: After phone-screen, individuals will be invited to an orientation session, where we will provide information about the study design, procedures, and risks/benefits. Individuals interested in participation will be consented, and scheduled for run-in visits. Run-in visits: The purpose of the run-in visit is to ensure participants are able to make the time commitment to come to ECU approximately three times per week. In our past training studies, this run-in period has helped to obtain excellent training adherence by allowing potential participants to fully evaluate their ability to commit to study time demands. To simulate participation in HI-PACE, run-ins sessions will be scheduled 3 sessions per week over the course of one week, and duration will be similar to training sessions (~30-60 minutes). Study staff will verify sedentary status, and screen for other inclusion/exclusion criteria (e.g. medical history questionnaire/study surveys, BMI, waist circumference, blood pressure assessment, etc.). As a safeguard against low exercise adherence, participants will complete an exercise calendar (identification of expected exercise days/times, and potential back-up times). Participants will also complete a questionnaire on time commitments, child/elder care, distance from the exercise facility, motivations for exercise, family support.

Phone Screening : Age (40-65 yrs.), BMI (30-45), Diabetes (NO), Heart disease (NO), sedentary, African American (YES), Contact info

Orientation

-Informational session about study requirements -Obtain consent for screening and run-in visits

Run-in visits

-3 run sessions over 1 weeks to test participants ability to come to ECU 3 times per week - Verify inclusion criteria (ie: baseline physical activity, waist circumference, blood pressure). -Collection of FFQ and QOL questionnaires

SV1

- Obtain consent for main study - Physical exam/review of medications -Lipids, CBC, Chem panel, insulin

Baseline

- Weight, blood pressure, anthropometry, CRP, DEXA, Exercise test, mitochondrial measurements, muscle biopsy, IVGTT, FFQ, QOL -Randomization (CON, LOW-INT, HIGH-INT)

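### The blood pressure exclusion joins its two limits with *and*, so a candidate over only one of them (such as 210/95 or 175/115 mmHg) is not excluded

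*Combined protocol and SAP*

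**What the plan says.** Section 3 (Approach), Inclusion/exclusion criteria, excludes people with "excessively high resting blood pressure (systolic >180 mmHg and diastolic >100 mmHg"). The same paragraph lists the additional diabetes risk factors, any one of which qualifies an obese candidate. Raised blood pressure is among them, with a systolic limit of "130 mmHG or diastolic" pressure of at least "85 mmHg or the use of BP medication". The qualifying limits are therefore joined by *or* and the excluding limits by *and*.

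Two other provisions bear on a hypertensive candidate:

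- The same list of exclusions ends with "conditions that are contraindicated for exercise", which is not defined further.
- Under Run-in visits (Section 5), "Study staff will verify sedentary status, and screen for other inclusion/exclusion criteria", and a blood pressure assessment is among the items named. Figure 3 adds a physical exam and medication review at screening visit 1 (SV1), and a blood pressure reading at baseline. None of these steps states a limit of its own.

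On exposure, the Maximal Exercise Test paragraph says: "Treadmill grade will be increased by 2.5% every 2 minutes until volitional exhaustion". The Specific Aims give the timing of the fitness outcome, "which will be assessed at baseline, mid-intervention, and follow-up". HIGH-INT participants train at the heart rate for 70-80% of VO₂ max, and the exercise-time table assumes three sessions a week.

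**The concern.** A numerical exclusion for resting blood pressure exists to keep people with very high pressure away from maximal exertion. Either component alone can be very high. A rule that needs both to be exceeded accepts an unlimited systolic value if diastolic is 100 or below, and an unlimited diastolic value if systolic is 180 or below.

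It would be easy to assume that staff will read the clause as *either*. The text gives them reason not to, because the same paragraph uses *or* for blood pressure where either value is enough. A screener applying the criteria exactly as written would be right to pass 175/115.

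What is at stake is participant safety. The baseline treadmill test comes before randomization, so a candidate who passes is tested to exhaustion whichever group follows. The validity of the CRF comparison is not at stake: eligibility is settled before allocation and applies equally to all three groups.

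**Working it through.** **Step 1. Apply the rule to specific readings.** S is resting systolic and D resting diastolic pressure, in mmHg.

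| Reading | S > 180 | D > 100 | Excluded as written (*and*) | Excluded with *or* |
|---|---|---|---|---|
| 210/95 | yes | no | no | yes |
| 175/115 | no | yes | no | yes |
| 185/105 | yes | yes | yes | yes |
| 175/95 | no | no | no | no |

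All four readings also meet the qualifying blood pressure risk factor (S ≥ 130 or D ≥ 85).

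**Step 2. Look for another limit.** The run-in check refers back to these same criteria. The SV1 exam, the baseline reading, the maximal test and the training sections give no blood pressure value. The clause in Section 3 is the only numerical blood pressure exclusion in the document.

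**Step 3. Count the exposure.** Maximal tests: baseline, week 12 and week 24, so 3. HIGH-INT sessions: 3 per week × 24 weeks = 72.

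**Step 4. How many candidates fall in the gap.** The plan gives no blood pressure distribution and no figure of its own to reproduce. The counts below rest on an assumed bivariate normal distribution with correlation 0.5 to 0.8. The mean/SD pairs are assumptions:

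- low: S 125/14, D 80/9
- middle: S 132/16, D 84/10
- high: S 140/18, D 88/11

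The formulas are:

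- P(S > 180) = 1 − Φ((180 − mean)/SD), and likewise for P(D > 100)
- P(both) = bivariate normal upper tail at the given correlation
- P(either) = P(S > 180) + P(D > 100) − P(both)
- passed per 60 = 60 × (P(either) − P(both))
- share excluded by the written rule = P(both) / P(either)

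For the middle case, (180 − 132)/16 = 3.0 gives P(S > 180) = 0.0014, and (100 − 84)/10 = 1.6 gives P(D > 100) = 0.0548.

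| Quantity | Low | Middle | High |
|---|---|---|---|
| P(S > 180) | 0.00004 | 0.0014 | 0.0131 |
| P(D > 100) | 0.0131 | 0.0548 | 0.1377 |
| P(both) | 0.00002-0.00004 | 0.0007-0.0013 | 0.0077-0.0123 |
| P(either) | 0.013 | 0.055 | 0.139-0.143 |
| Over a limit but passed, per 60 | 0.8 | 3.2-3.3 | 7.6-8.1 |
| Share excluded as written | 0.1-0.3% | 1.3-2.3% | 5.4-8.9% |

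Ranges are over the correlation and come from unrounded probabilities.

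**Step 5. Who they are.** Nearly all have D > 100 with S ≤ 180; systolic-only cases are at most 0.33 per 60. Because S > 180 is much the rarer event in all three scenarios, requiring both makes the diastolic limit almost inert. About 81-97% of those passed have D between 100 and 110. D ≥ 115 with S ≤ 180 occurs in 0.003 (low), 0.04-0.05 (middle) and 0.21-0.35 (high) per 60, and S ≥ 210 in at most 0.003 per 60.

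**The case against.** The strongest reply is that this is loose wording with little consequence. The parenthesis can be read as listing the cut-off for each component, and a clinician would be unlikely to send someone at 210/95 to a maximal test. Eligibility requires passing every exclusion, including the undefined ones for significant medical conditions and contraindications to exercise. Blood pressure is looked at during run-in and again at baseline, and there is a physical exam in between. Section 9 promises a manual of procedures and standard operating procedures before recruitment, which may contain working limits.

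The size can also be challenged. The distribution is assumed and the result spans about tenfold. Most of the candidates counted are modestly over the diastolic limit, and nothing in the document shows that 101-110 mmHg makes supervised exercise unsafe. Raised blood pressure is only one of several qualifying factors, and medication users may be well controlled, so it is not certain that recruits sit close to the limits. Only a third of those randomized go to HIGH-INT.

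Much of this stands as a limit on the consequence. The extreme readings show how the rule works and are not typical cases. The counts are per 60 candidates before clinical judgement, so they do not predict enrolments. None of it repairs the criterion. The other safeguards name no limit, so they give a screener no number to set against a numerical rule that passes the candidate. As for intent, if *or* was meant, the text says something else; if *and* was meant, the plan accepts a resting 175/115 for maximal exertion and gives no reason.

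**Conclusion.** The concern holds. As written, the only numerical blood pressure exclusion does not exclude a candidate over a single limit. That follows from the text alone and needs no assumption.

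How often it would matter is uncertain. Under the assumed distributions, roughly 1 to 8 of every 60 otherwise eligible candidates would be over a limit and not excluded by this rule, mostly through diastolic pressure a little above 100. An unknown share would be stopped by clinical judgement. The criterion should be corrected because a safety threshold that is applied correctly should not admit people over one of its own limits. Confidence in the practical size is moderate.

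**What to change.** In Section 3, Inclusion/exclusion criteria, change the exclusion to systolic >180 mmHg *or* diastolic >100 mmHg. With that wording 210/95 and 175/115 are excluded, 185/105 stays excluded and 175/95 stays eligible.

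Two additions would help, though the correction does not depend on them: refer a candidate over either limit for clinician review, with re-screening allowed once both values are below the limits; and use the same either-limit rule to defer a maximal test whenever a resting reading is taken beforehand.

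The correction itself is one word; the additions need a short procedure and some clinician time. Under the assumptions above, 1-14% of otherwise eligible candidates would be deferred or excluded, some recoverable. In the worst case, enrolling 60 needs about 60 / (1 − 0.14) ≈ 70 otherwise eligible candidates. Section 4 says the recruiting core has enrolled more than "400 African American adults" a year for research. That figure covers research generally and not people eligible for this trial, but it suggests that about ten more candidates is a manageable demand. The sample size, power and analysis are unaffected.

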Mid-Intervention

-Anthropometry, Weight, Treadmill fitness test

Follow-up

	Weight, blood pressure, anthropometry								
	-DEXA, Exercise test, mitochondri	ondrial							
ł	measurements, muscle biopsy								
	-Lipids, insulin, CRP, IVGTT	Figure 3.							
	-FFQ and QOL questionnaire	Study Flow							

Screening visit 1 (SV1): At SV1, fasting blood draws will be performed to evaluate hepatic, renal, hematological, endocrine, lipids, blood chemistries, and metabolic function for inclusion/exclusion purposes. Pre-menopausal women will take a pregnancy test.

Assessment visits: We will obtain primary (CRF) and secondary outcome measures (IVGTT, DEXA, QOL, mitochondrial measures) at baseline and follow-up (24 weeks) (Figure 3). At mid-intervention (week 12), CRF, body weight and anthropometry will be evaluated. At follow-up (week 24), we will re-evaluate all outcomes measures. Randomization (stratified by sex) will occur at the completion of baseline assessments. Additionally, a blood sample (~10 mL) will be obtained at baseline and follow-up and archived at -80°C for future analysis. Exercise intervention: All exercise sessions will be supervised by study staff at the FITT Center (open: 12.5 hrs. Mon-Fri [2.5 hrs.: Sat.], and Heart Institute exercise facilities (open: 6 hrs. Mon-Thurs [4 hrs. Fri.]). All exercise will be performed on a treadmill to maintain close control over kcal expenditure. Participants in the MOD-INT group will exercise at the heart rate associated with 45-55% VO₂ max, and participants in the HIGH-INT group will exercise at a heart rate associated with 70-80% VO₂ max (heart rate ranges will be updated at mid-intervention CRF assessment). The exercise volume for both groups will be 600 MET-minutes per week, which is consistent with current public health guidelines (500-1,000 MET-minutes)³. Since all participants will be sedentary at baseline, we will gradually increase the volume of training. All participants will exercise at 300 MET-minutes during week 1. The volume of exercise will increase 50 MET-minutes per week until they reach the maximum exercise volume of 600 MET-minutes (week 7). Using standard American College of Sports Medicine (ACSM) equations, we will calculate the amount of MET-minutes exercised based on treadmill speed/grade and the participants' weight ⁶¹. Laptop carts with custom-made spreadsheets will be used to track MET-minutes, exercise training data, and aggregation of weekly values (mean RPE, speed, grade, caloric

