
physical activity, and charge status of all active devices in the study. We will utilize food frequency questionnaires (FFQ) ⁶² to measure estimated daily intake (kilocalories, macronutrients, and micronutrients). 7. Statistical Considerations: Initial CRF will be compared for the three groups using side-by-side boxplots. Side-by-side boxplots will also be made for males and separately for females as we expect the max O2 to be greater for males. Numerical summaries for the boxplots along with mean and standard deviation will be recorded. Outliers and other observations requiring additional scrutiny will be identified. These steps will be repeated for the measurements taken post intervention and for the differences. The groups will be compared in terms age and other covariates using graphs (boxplots for numeric variables and segmented bar plots for categorical data) and numeric summaries. Assuming the descriptive analyses reveal no serious violations of the assumptions, ANOVA will be used to analyze the differences in CRF. In addition to using contrasts for group comparisons, confidence intervals for the difference in means will be reported. Both one-way (factor Group) and two-way (Group and Sex) ANOVA will be used. The analyses described for CRF would also be applied to insulin sensitivity, and other secondary outcomes. Data will be analyzed on an intention to treat basis. We expect attrition rate to be approximately 10-15%. Using -.112, .124, and .200 L/min as the means for the three groups based on previous data ³⁵, a common standard deviation of .250 L/min, and significance level .05, the power ranges from .85 for 15 participants per group to .96 for 20 participants per group. 8. Experience of PI: The PI has 33 publications on exercise training and T2D/CVD risk factors, and is a former NIDDK T-32 postdoctoral fellow (Pennington Biomedical, Mentor: [name].). He has worked on a completed trial on exercise intensity and visceral fat ⁶³. His publications include 3 papers on exercise intensity ^{35,64,65}, 5 papers on racial health disparities ^{9,21,66-68}, and 4 papers dealing with cardiorespiratory fitness as a risk factor for disease ^{21,65,69} (3 specifically on CRF in adults with T2D ⁷⁰⁻⁷²), and a recently published review paper on racial disparities in T2D²⁶. He has been awarded an NIH loan repayment award from NIMHD, and was recently accepted to the NHLBI sponsored PRIDE summer research program for health disparities research. 9. Potential Pitfalls: Recruitment of the necessary sample of African Americans is a potential concern. However, the CHD has documented success with recruitment of African Americans. The PI and the CHD will closely monitor recruitment trends. If the recruitment of participants is below the expected rate, we will develop new recruitment plan to meet the necessary study sample. As the PI is a second year faculty member, another potential pitfall is that the study team has not worked extensively together on a clinical trial. As noted in the study flow diagram (below), during start-up, extensive study planning will take place inclusive of a manual of procedures (MOP), standard operating procedures (SOP), and simulations of data collection of all study visits/databases prior to the start of recruitment. Additionally, Drs. [name] and [name] are co-investigators on the PI's ongoing AHA funded exercise trial at ECU, which currently has 92% exercise adherence (6 month exercise intervention), which suggests the PI is capable of implementing an exercise intervention at his new institution. While the PI will assume complete responsibility of leading this trial, [name] (expertise: large exercise trials/insulin sensitivity, muscle biopsies) will serve as faculty mentor, and the research team will engage in regular study meetings to closely monitor the progress of important indicators of study success (e.g. recruitment rates, adherence to exercise levels and intensity, etc.). If the results of HI-PACE are not supportive of what we have hypothesized on CRF, the secondary measures (insulin sensitivity, skeletal muscle measures, body composition) and archived blood/muscle samples are potential sources to support an R01 application. 10. Conclusion: The HI-PACE study has high public health relevance due to the increased disease burden of T2D and the lack of exercise training studies in African Americans. HI-PACE will be the first study to compare two exercise training programs on T2D risk factors in obese African Americans, and has the potential to influence future physical activity recommendations. We will also obtain valuable psychological parameters of quality of life and enjoyment of exercise, which will help determine whether high intensity aerobic exercise is a feasible strategy over a six month period to improve health outcomes in African Americans. In accordance with the goals of this funding mechanism, the specific direction of the R01 will be dependent on the results of the

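### Quality of life is listed twice before randomisation, but the run-in value has no stated use and the planned change score is not the most precise analysis

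*Combined protocol and SAP*

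**What the plan says.** In the study flow (Figure 3), the run-in box includes "Collection of FFQ and QOL questionnaires". The Baseline box lists the questionnaires again and ends with allocation: "IVGTT, FFQ, QOL -Randomization (CON, LOW-INT, HIGH-INT". The follow-up box has one further collection: "FFQ and QOL questionnaire".

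The text on assessment visits (Section 5) fixes the order: "Randomization (stratified by sex) will occur at the completion of baseline assessments". Both early collections therefore precede allocation. The same text begins "We will obtain primary (CRF) and secondary outcome measures (IVGTT, DEXA, QOL" and places these measures at baseline and follow-up; it does not mention run-in.

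Section 3 names quality of life among the main secondary outcomes, measured by the SF-36. In Section 7, "ANOVA will be used to analyze the differences in CRF", by one-way (group) and two-way (group and sex) models, and the same approach is extended to insulin sensitivity and the other secondary outcomes. Section 7 mentions neither a baseline covariate nor any use of a second pre-randomisation value.

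The food frequency questionnaire (FFQ) appears in the same boxes. Section 6 gives its purpose as estimating daily intake. It is not named as a secondary outcome.

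**The concern.** A change score carries the full measurement noise of the one initial value into the comparison between arms. Here a second pre-randomisation value appears to be collected and is given no analytic role. Neither questionnaire score is a stated eligibility criterion and both precede allocation, so using both scores cannot bias the comparison.

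The stake is precision on a small sample. Section 7 expects 10-15% attrition from 20 per arm, which leaves 17-18. Section 10 looks to quality of life to help judge whether high-intensity exercise is feasible over six months. A wide interval would make that judgement weak.

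**Working it through.** **The plan's own figure.** There is none for quality of life. The only power statement concerns fitness (CRF): 0.85 at 15 and 0.96 at 20 per group. The omnibus F test with the stated means and SD gives 0.878 and 0.957. Nothing below rests on it.

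**Inputs.** From the documents: two listed pre-randomisation collections, one follow-up, a change-score analysis, 17-18 completers per arm. Assumed, because the documents give no value: equal variance (set to 1) at each time; r, the correlation of each early score with week 24; r12, the correlation between the two early scores.

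**Residual variance of each analysis**

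- Planned change from one value: 2 − 2r
- Change from the mean of two: 1 + (1 + r12)/2 − 2r
- ANCOVA on one value: 1 − r²
- ANCOVA on the mean of two: 1 − r²/[(1 + r12)/2]

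The standard error (SE) moves with the square root of the variance ratio.

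**At r = 0.6.** The planned analysis has variance 2 − 1.2 = 0.80. ANCOVA on the Baseline value alone has 1 − 0.36 = 0.64, and √(0.64/0.80) = 0.894, so the SE is 10.6% smaller.

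| r12 | Change from mean: variance | SE reduction | ANCOVA on mean: variance | SE reduction |
|---|---|---|---|---|
| 0.60 | 0.600 | 13.4% | 0.550 | 17.1% |
| 0.70 | 0.650 | 9.9% | 0.576 | 15.1% |
| 0.80 | 0.700 | 6.5% | 0.600 | 13.4% |
| 0.90 | 0.750 | 3.2% | 0.621 | 11.9% |
| 0.95 | 0.775 | 1.6% | 0.631 | 11.2% |

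All reductions are against the planned 0.80. Beyond single-baseline ANCOVA, the second score adds 7.3% at r12 = 0.60, 3.2% at 0.80 and 0.7% at 0.95.

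**Other values of r.** ANCOVA on the mean against the planned change score gives 16.5-19.0% at r = 0.4 (r12 from 0.95 to 0.5) and 7.3-15.0% at r = 0.8 (r12 from 0.95 to 0.8).

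**Run-in less predictive than Baseline.** With unequal correlations the change from the mean has variance 1 + (1 + r12)/2 − r(Baseline) − r(run-in). Its gain is zero when r(Baseline) − r(run-in) = (1 − r12)/2. Take r12 = 0.8:

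- 0.60 against 0.50: 1.9 − 1.1 = 0.80, no gain.
- 0.60 against 0.45: 1.9 − 1.05 = 0.85, and √(0.85/0.80) = 1.031, so the SE is 3.1% larger.

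In that last case ANCOVA on the mean has variance 1 − 0.525²/0.9 = 0.694. This still beats 0.80 (SE 6.9% smaller) but is worse than Baseline alone at 0.64. With the two scores as separate covariates it is 1 − (0.36 + 0.2025 − 0.432)/0.36 = 0.6375, so nothing is lost before degrees of freedom are counted.

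**Cost in degrees of freedom.** With 51 completers and a model with group and sex, 51 − 4 = 47 residual degrees of freedom remain. Chance imbalance inflates the variance on average by about 1 + 1/45 for one covariate and 1 + 2/44 for two, that is about 1.1% and 2.2% on the SE. At r = 0.6 the net reduction is then 9.6% for Baseline alone, 10.2-16.2% for the mean, and 9.2-15.2% for two covariates. If r12 is near 0.95, the second score adds almost nothing.

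**The case against.** Several objections have force.

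- **Two usable scores are not proven.** The two listings could be one form handed out at run-in and returned by Baseline, or the run-in forms could serve screening. The text shows neither, but the sponsor must confirm. With one administration the run-in point falls away; the gain from baseline adjustment remains.
- **Consent.** Figure 3 shows consent for screening and run-in before consent for the main study. Whether the former covers outcome analysis cannot be seen, because consent pages were removed. This needs checking and is not a shown bar.
- **The baseline is not really ambiguous.** Figure 3 has a visit called Baseline that lists quality of life, so the natural reading of the text identifies that value. This is fair. A reader might infer that the plan discards the run-in score, but it is only silent on it.
- **Averaging need not help.** A reader might take the best case, variance down 25% and SE down 13.4%, as the expected gain. That requires the two early scores to correlate no better with each other than with a score about 24 weeks later, which is unlikely if they are closely spaced. The gain can also vanish or reverse.
- **Diet.** A reader might infer that the FFQ is analysed by the same change score. No comparison of diet between arms is stated, so the documents do not support this.
- **Materiality.** A single baseline is ordinary practice, and only a secondary outcome in a 60-person pilot is involved. This stands, and sets the weight of the point.

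**Conclusion.** The point holds as an optional, nearly free improvement in precision. Quality of life is listed twice before allocation, the planned analysis is an unadjusted difference, and the run-in score has no stated use. At an assumed r = 0.6 and r12 = 0.6-0.95, ANCOVA on the mean of the early scores has an SE about 11-17% below the planned analysis, or about 10-16% after the cost in degrees of freedom. Baseline adjustment itself supplies 10.6% of this. The run-in score adds between under 1% and about 7%.

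These sizes rest on assumed correlations, equal variances and two genuine administrations. The planned analysis remains valid, and the primary CRF comparison is unaffected.

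**What to change.** Ask the sponsor whether quality of life is administered separately at run-in and at Baseline, and whether the run-in consent covers its use. If it is a single form, correct Figure 3.

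Then, before follow-up data are seen, add to Section 7: week-24 quality of life will be analysed by ANCOVA with group and sex, adjusted for pre-randomisation quality of life. Choose one form in advance, either the Baseline and run-in scores as two covariates or their mean, and use the single available score if only one exists. Two covariates guard against a weakly predictive run-in score; the mean saves a degree of freedom. If there is only one administration, adjust for that score.

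State also whether the arms will be compared on FFQ intake. If so, apply the same baseline definition.

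The cost is a sentence or two in Section 7 and one or two degrees of freedom, with no new visits or data.
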